### **7. Sharing of Results with Participants**

Subjects will receive a copy of the laboratory screening done at study entry and asked to follow up with their primary care providers further to discussion of those results.

### **8. Study Duration**

Individuals will be in the study for about 3-4 months each. We anticipate screening 500 subjects to enroll 50 for this protocol over 12-14 months. The duration anticipated to complete all study procedures and data analysis is expected to be 6 months after the last subject is enrolled; the study duration for the entire study is expected to be about 2 years.

### **9. Vulnerable Populations**

- Children
- Pregnant women/Fetuses/Neonates
- Prisoners
- Adults lacking capacity to consent and/or adults with diminished capacity to consent, including, but not limited to, those with acute medical conditions, psychiatric disorders, neurologic disorders, developmental disorders, and behavioral disorders

- Non-English speakers
- Those unable to read (illiterate)
- Employees of the researcher
- Students of the researcher
- None of the above

Adults must have the capacity to self-consent to be in this study.

## **10. Recruitment Methods**

- a. Recruitment Process: Subjects will be approached in person by Co-investigators [name] or [name] when they present for Move Mass appointments and will be directed to call the Study Coordinator for more study details and to set up their consent visit. Subjects may also self-identify after seeing posters or flyers posted in the Minneapolis VAMC facility and contact the investigator team. Subjects may also contact the study team after hearing about the study from other providers at the Minneapolis facility. Consenting will take place in a private setting at the Minneapolis VAMC. Subjects may take as long as needed to decide whether or not to participate once they have heard about the study-related details from the investigative team and study staff will emphasize the voluntary nature of participation and that whether or not a subject participates has no bearing on clinical care provided by the VAMC.
- b. Source of Participants and identification of potential participants: Subjects will be recruited from the Minneapolis VAMC and surrounding CBOC's patient population via clinical contact with the study investigators, or by self-identification after seeing flyers/posters or after hearing about the study from their other providers at this facility. Subjects who expressing interest in the study and appearing to meet the eligibility criteria and agreeing to medical record review for the purposes of this study will then have their medical records reviewed to further assess study eligibility.
- c. Payment:

Due to the commitment of time, and the potential for transportation costs and lost wages due to participating, subjects will be compensated for their study participation at a rate of \$15 per hour. If a subject completes only part of a visit they will be compensated at a rate of \$10 per hour, prorated for the time spent in that visit.

## **11. Withdrawal of Participants**

- a. Withdrawal Circumstances: Subjects are free to withdraw from the study at any time and they may be withdrawn by the study investigators if it is deemed that it would not be safe for them to continue with the study or if subjects are not following the study-related procedures which would compromise the scientific integrity of the study.

b. Withdrawal and Termination Procedures: If a subject wishes to withdraw or is asked to withdraw from the study the participant would be asked to participate in an early end-of-study visit (procedures to be followed would be those of V8) and the subject would be asked about continued data collection of clinical data (vitals and medications) to finish out the period of time they would have participated in the study. All data collected up to the period of withdrawal or termination and as arranged with the subject through partial withdrawal would continue to be used as per study-related purposes.

## **12. Risks to Participants**

a. Foreseeable Risks:

Physical—tDCS is considered to be a safe brain stimulation modality which is rarely associated with adverse events and there is no evidence of serious side effects. Subjects will be discontinued from the study if they develop sores at the administration site or headaches which impair global functioning. Milder side effects that subjects could experience include itching at the site, nausea, milder headaches, and fatigue. Subjects may choose to discontinue stimulation at the session at any time they experience discomfort or side effects. We will be utilizing the standards which have been utilized previously for this modality; trained study staff will administer the treatment sessions.

Psychological—Questionnaires as well as the tDCS active vs. sham treatments are utilized during the visits; subjects could experience mental fatigue related to the testing.

Social—there is no anticipated social risk to participating.

Economic—Subjects could incur financial risks related to transportation and lost wages while participating; for this reason, study compensation is provided to help minimize this risk.

Legal-- there is no anticipated legal risk to participating

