## 6. Study Methods, Procedures, and Statistical Plan

### Study Design:

For this single-site pilot study our statistical approach will be similar to prior work done by members of our team previously, a double-blind, randomized controlled design with participants randomized to either active or sham tDCS. For this study Veterans will be referred as potential candidates because they have obesity and self-report that they tend to have at least one occasion of out-of-control eating per week on average. Participants will be trained on the Brain HQ, an interactive computer software package in which subjects work through a series of structured exercises designed to stimulate neuroplasticity. Participants will be randomly assigned to receive either active tDCS or sham stimulation with their training during one hour session each day( 13 minutes of stimulation , 20 minute stimulation break, followed by 13 more minutes of stimulation) over five days. A 2 mA current will be applied with two 25 cm^2 saline soaked electrode sponges with anode at F4 (right) and cathode at F3 (left) concurrent with the Brain HQ. To evaluate generalization, an untrained NIH Examiner Battery sub-set testing 4 modalities of executive function will be performed before and after the five days of training. Subjects will then go through the Move Mass Behavior Modification after completing the five days of treatment. (This 16-week structured behavior modification program of bi-weekly sessions is usual care for these participants.) Participants will return for the trained and untrained testing at V7 (halfway through the behavior modification course) and V8 (final study visit to occur after the behavior modification course) follow-up sessions without stimulation. For the trained Brain HQ tasks, growth curve analysis (GCA) examining individual variation of the

growth rates over time will be done (across the 5 days of tDCS sessions and the subsequent follow-ups) to examine for change in individual and group trajectories over time. For the untrained NIH Examiner tasks, GCA will be used to evaluate for individual and group effects in executive function in the four domains of the NIH Examiner Battery from pre- to post-treatment and through follow-up sessions. We will also compare pre- and post- treatment results in the cravings and binging questionnaires within and between groups.

Figure 1: Study Visit Schedule

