## **17. Discontinuation criteria**

- Sores at the tDCS site
- Headaches that impair global functioning

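### Scalp sores or impairing headaches end study participation, not only stimulation, so the stimulation-free follow-up outcomes can be lost; a minor gap that is cheap to close

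*Combined protocol and SAP*

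**What the plan says.** Section 12 (Risks to Participants) sets two rules. For the more serious effects: "Subjects will be discontinued from the study if they develop sores at the administration site or headaches which impair global functioning". For other effects: "Subjects may choose to discontinue stimulation at the session at any time they experience discomfort or side effects". The protocol thus separates leaving the study from stopping the current, and applies the former to sores and impairing headaches. Section 17 (Discontinuation criteria) repeats both criteria, for example "Headaches that impair global functioning", without saying what is discontinued.

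Section 11 (Withdrawal of Participants) covers people who are asked to withdraw. They are invited to one early end-of-study visit with V8 procedures. For the rest of their planned time, "the subject would be asked about continued data collection of clinical data (vitals and medications"). Data already collected are kept, and data "as arranged with the subject through partial withdrawal would continue to be used as per study-related purposes".

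V7 and V8 are "follow-up sessions without stimulation" (Section 6, Study Design). Table 1 lists Examiner, BES, Brain HQ and weight at both. The Section 6 growth curve analysis of the Examiner runs "from pre- to post-treatment and through follow-up sessions". The Statistical Plan tests a group-by-time interaction for weight, and Section 4 (Study Endpoints) makes weight change over the study period the secondary endpoint.

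**The concern.** The hazard is the current, and stopping the current removes it. V7 and V8 deliver none, so a stimulation side effect is not in itself a reason to cancel them. As written, someone who develops a sore in the stimulation week leaves the visit schedule before the 16-week programme starts. An early visit at that point cannot show weight at the end of the programme, or cognition and eating behaviour at two and four months.

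The loss may also differ by arm. Active treatment is 2 mA for 13 minutes in each of ten periods. Sham is a 30-second ramp-up followed by immediate ramp-down at the same electrode sites. If more active than sham participants are removed, and they would have fared differently, the follow-up comparison of Examiner and BES, and possibly of weight, rests on a selected active group.

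**Working it through.** The plan gives no event rate, dropout allowance or bias figure on this point, so there is nothing of its own to reproduce. Its power statement does not enter.

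**What is collected after removal**

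| Outcome | Early visit | Scheduled V7 and V8 |
|---|---|---|
| Examiner, BES | asked for | not named |
| Weight | asked for | only if vitals includes it |
| Medications | not separately named | asked for, with agreement |

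These events should mostly arise in the stimulation week, so the early visit would probably fall near V6. The primary comparison in the Statistical Plan is change before and after training, and that visit largely preserves it.

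**Inputs from the documents.** Ten per arm (Study Summary); up to 50 consented so that 20 complete (Section 6, Study Procedures); Table 1 payments.

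**Assumptions.** Participants removed from the active arm would have scored 0.5-1.0 SD worse at V8 than those retained. Active-arm event rate 2-5%, sham rate zero. Correlation between visits 0.5-0.7.

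**1. Completer comparison, near worst case.** Bias = (share of the active arm removed) x gap.

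- One removed and replaced, so 1 of 11: 0.5/11 = 0.045 to 1.0/11 = 0.09 SD. Ten still complete in each arm, so the standard error does not widen. Two-sided type I error (noncentral t, 10 v 10) is 5.1-5.4%.
- One removed and not replaced: 0.1 x 0.5 = 0.05 to 0.1 x 1.0 = 0.10 SD. The standard error is wider by sqrt(1/9 + 1/10)/sqrt(2/10) = 1.027. Type I error is 5.1-5.5%.
- Two removed and replaced: 2/12 x 0.5 = 0.083 to 2/12 x 1.0 = 0.167 SD. Not replaced: 0.10-0.20 SD, standard error ratio 1.061, type I error 5.5-6.8%.

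**2. Repeated-visit model that keeps baseline and the early visit.** With equal correlation rho between visits, and a gap that shows at the early visit but not at baseline, the model recovers rho/(1 + rho) of it. The remaining bias is share x gap/(1 + rho). For one replaced removal this is 0.045/1.7 = 0.027 to 0.091/1.5 = 0.061 SD. For one not replaced it is 0.05/1.7 = 0.029 to 0.10/1.5 = 0.067 SD.

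**3. How often.** Among ten active participants, P(at least one) = 1 - (1 - p)^10 = 18% at p = 0.02 and 40% at p = 0.05. P(two or more) = 1.6% and 8.6%.

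**4. Expected bias.** p x gap = 0.02 x 0.5 = 0.01 to 0.05 x 1.0 = 0.05 SD in the near worst case. Dividing by (1 + rho) gives 0.01/1.7 = 0.006 to 0.05/1.5 = 0.033 SD. The standard error of a difference with ten per arm is sqrt(2/10) = 0.447 SD, so 0.006-0.05 SD is about 1-11% of one standard error.

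If those removed would have done better, the sign reverses. Equal removal of similar people in both arms gives no bias.

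**The case against.** The strongest reply is that Section 11 already handles most of this. It seeks a full V8-type assessment at withdrawal, may recover later weight through vitals, and leaves room for more by individual arrangement. The sure loss is then the scheduled V7 and V8 Examiner, BES and Brain HQ. Section 14 also describes the Examiner growth curve only from before to after treatment. This stands, and it limits the point to follow-up and weight.

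The trigger should also be rare. Study Subjects (Section 6) excludes people with frequent severe headaches or a history of scalp conditions. Impedance is checked before each session and every second during it, and stimulation stops above the limit. Section 12 calls tDCS "rarely associated with adverse events". The assumed 2-5% makes no allowance for these safeguards. Sham participants wear the same sponges at the same sites, so some sores could arise in either arm. All of this stands.

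A reader might infer that each removal costs a tenth of an arm and widens the standard error. The documents do not support that. Enrolment aims for 20 completers from up to 50 consented, so a removed participant may be replaced. Replacement restores precision but does not undo selection. No replacement rule is spelled out, which is why both cases are shown above.

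What the objection does not answer is that Section 12 says participation ends, and that no text places these participants back on the V7 and V8 schedule for Examiner and BES.

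**Conclusion.** The gap is real but minor. Followed as written, the plan can lose stimulation-free follow-up outcomes for a side effect that may be related to arm. The likely bias is small: about 0.045-0.09 SD for one replaced removal in a completer comparison, and 0.006-0.05 SD in expectation. These sizes rest on the assumed gap, event rates and correlations. The documents supply none of them, and the direction is unknown.

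Two stronger readings are not supported. A reader might infer that the primary result is compromised or tilted towards tDCS; it is largely protected by its pre-post definition and the early visit, and nothing fixes the sign of any bias. A reader might also infer that the early visit will be analysed as V8, or that weight will be analysed in completers only; the documents say neither. Which participants form the analysis set is a separate question that this point does not settle.

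**What to change.** - **Section 12:** keep both criteria, but say that stimulation is stopped and study follow-up continues.
- **Section 17:** state that the criteria discontinue stimulation.
- **Section 11:** invite these participants to the remaining scheduled V6-V8 assessments (Examiner, BES where scheduled, weight) unless they withdraw consent or attendance is unsafe. Name weight in the continued collection.

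The cost is protocol wording and a few visits that are already planned. At Table 1 rates, participant payment is $30 + $30 = $60 per affected person for V7 and V8, and at most $22.50 + $60 = $82.50 if V6 is still due. Staff time is extra and is not given in the documents. No stated sample size or test changes.

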## **13. Potential Benefits to Participants and Society**

Potential Benefits: There is not potential for direct benefit other than as related to a decrease in food impulsivity but there is no guarantee of direct benefit. Societal benefits could include providing better treatment for conditions related to impulsivity.

## **14. Data Management**

Data Analysis Plan: For this pilot study participants will be randomized to either active or sham tDCS. For the trained task, growth curve analysis (GCA) examining individual variation of the growth rates over time will be done (across all 10 tDCS sessions and the subsequent follow-ups) to examine for change in individual trajectories over time. For the untrained task (NIH Examiner), GCA to evaluate for enhancement of executive function in the four domains from pre- to post-treatment as compared with the sham group will be analyzed. As a secondary aim we will evaluate weight loss response during and after the behavior modification program

and evaluate the effect of active vs. sham treatment on weight loss. Results from this study will inform larger follow up studies supported by external applications.

## **15. Data security**

All PHI will be kept in a secure database behind the VA firewall. Any paper records will be stored in a locked file cabinet accessible to study staff only. Data from each subject will be assigned a unique study identifier with the key available only to study staff, stored in secure database behind the VA firewall. Patient identifiers may only be disclosed to the study's finding entities for reporting and record keeping purposes as required by law. Any data that may leave the Minneapolis VAMC will be de-identified.

## **16. Provisions to Monitor the Data to Ensure the Safety, privacy, and confidentiality of Participants**

Data privacy and confidentiality protection are described above. The study will also have an external study monitor, [name], whose roles may include reviewing the study protocol and recruitment procedures with study staff, monitoring tDCS device utilization, and following up with any subjects and the IRB regarding any adverse events which occur.

## **17. Discontinuation criteria**

- Sores at the tDCS site
- Headaches that impair global functioning

